8.3 Procedures at each visit

8.3.1 First Visit = Screening

The **first visit (screening visit)** at our outpatient clinic will take about 60min. We will explain the study and will make sure the candidate is eligible for this trial. The candidate must arrive on an empty stomach (not allowed to eat or drink 10 hours prior to this appointment except for tap water or unsweetened herbal tea without milk).

- We will ask questions about his/her general health and will explain the study in detail. We will
 also briefly examine the candidate (measurement of blood pressure, weight).
- In women of childbearing age (18-49 years old), who do not take any contraceptives we will carry out a urine pregnancy test.
- We will take a blood sample and examine HbA1C, creatinine, ALAT, ASAT, hsCRP and blood lipids.
- The participant will receive a faecal sample kit with detailed instructions on how to take a stool sample.

• The participant will receive a study folder with detailed instructions for the whole study. Included in this study folder is a food diary, which the participant will be asked to fill out during a 7 day period (before starting with the intake of the substance).

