4.2 Secondary Outcomes

- Human gut microbiota composition: Faecal samples will be taken before and after treatment and the taxonomic and functional profiles of the gut microbiota will be assessed by metagenomic shotgun sequencing.
- Metabolomics: Faecal and urine samples will be used for analysis of the metabolome using metabolomics.
- Blood lipid profile, hsCRP and hepatic enzymes: Fasting samples will be taken to measure triglyceride, total cholesterol, LDL and HDL levels, and the liver enzymes ASAT (aspartate transaminase) and ALAT (alanine transaminase). The analysis will be carried out in the hospital laboratory (St. Claraspital).
- **Inflammatory response:** As erythritol might act as a radical scavenger and reduce oxidative stress, we plan to assess inflammatory state by measuring IL-6, TNF-α, sTNFR1, sTNFR2, high sensitive CRP (hsCRP) and leucocytes.
- Intestinal permeability: Circulating markers of intestinal permeability (zonulin, LPS) will be measured.
- Gastrointestinal tolerance (bloating, diarrhoea etc.): We will assess gastrointestinal symptoms by using a validated questionnaire (Clinical rating scale for gastrointestinal symptoms: Svedlund et al.²¹). The questionnaire will be used at baseline and at the end of week 3 and 7 (self-reporting). A license agreement will be sent to AstraZeneca (ASTRAZENECA AB, 556011-7482 S-151 85 Södertälje, Sweden).
- 4.3 Intestinal Glucoseabsorption: We will assess intestinal glucose absorption by use of a validated technique: during the oral glucose tolerance test, 3g of 3-O-Methyl-Glucose (3-OMG) is ingested. 3-OMG is then measured in the plasma samples obtained at 0-30-60-90-120min. Other Outcomes of Interest

We accept that a possible confounder might be the substitution of sucrose in daily life as polyols might serve as a substitute. If sugar consumption is reduced, metabolic effects could be caused by reduced sugar exposure rather than polyol intake. We will therefore assess overall sugar consumption before and during the trial. Participants will keep a food diary. For this purpose we will use the clinical diary used by our nutritionists for preoperative assessment of bariatric patients.

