8.2 Assessments of outcomes

8.2.1 Assessment of primary outcome

Oral glucose tolerance test (OGTT):

At baseline and after the treatment period (ca. 49d plus 3 days) an oral glucose tolerance test is carried out.

Patients are instructed:

- that they should not have been acutely ill (acute infection of any kind) within 14 days prior to OGTT.
- to abstain from strenuous exercise within the last 48h before OGTT,
- to make sure their main meals within the last 48h before OGTT include carbohydrates,
- that they must not eat or drink, nor consume alcohol or smoke within 10 hours before OGTT.

Blood sampling: After an overnight fast of at least 10 hours an antecubital catheter will be inserted into a forearm vein for blood collection. After a fasting blood sample on ice into 7.5mL tubes containing EDTA (6 µmol/L) the participant will ingest a 75g glucose solution (300 ml OGTT syrup, Roche) within 5-10min.

Further blood samples will be taken at regular time intervals (30, 60, 90, and 120 min).

Tubes will be centrifuged at 4° C at 3000 rpm for 10 min and 4 plasma sample aliquots are pipetted into 1.5mL tubes (aliquots à 600μ L plasma each; tubes labelled: ① Insulin/Glucose, ② C-Peptide, ③ Reserve 1, ④ Reserve 2). Samples will be stored at -80° C until analysis of plasma glucose, insulin and C-peptide.

STANDARD ORAL GLUCOSE TOLERANCE TEST: DEFINITIONS

Diabetes Fasting plasma glucose ≥7.0mmol/l or ≥11.1mmol/l (OGGT: 2–h plasma glucose))

Impaired Glucose Tolerance (IGT) Fasting plasma glucose <7.0mmol/l and ≥7.8 and <11.1mmol/l (OGGT: 2-h plasma glucose)

Impaired Fasting Glucose (IFG) Fasting plasma glucose 6.1 to 6.9mmol/l and <7.8mmol/l (OGGT: 2-h plasma glucose)

- > OGTT: venous plasma glucose 2-h after ingestion of 75g oral glucose load

Definition and Diagnosis of Diabetes Mellitus and Intermediate Hyperglycaemia: Report of a WHO/IDF consultation. World Health Organization 2006

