8.3.2 Second Visit = 1. Metabolic Visit

The **second visit (1. metabolic visit)** at our outpatient clinic will take about 2.5 hours. We will carry out an oral glucose tolerance test and take blood, and urine samples. If possible, the participant will bring the first faecal sample to this visit. Again, the participant has to arrive on an empty stomach (not allowed to eat or drink 10 hours prior to this appointment except for tap water or unsweetened herbal tea without milk). Even chewing gum must be avoided, as they might contain sugar. In addition 2 days prior to the test the participant has to refrain from heavy physical activity and needs to have carbohydrates as part of her/his meals.

- The candidate will be assigned randomly to one of the three groups (intake of xylitol, or erythritol or control group).
- The participant needs to bring his/her study folder along, including the food diary which he/she should have kept over the course of 1 week.
- If possible, the participant will bring along the first faecal sample
- We will take a first blood sample to measure blood sugar, insulin, C-peptide (for the oral glucose tolerance test). In addition we will measure biomarkers of inflammatory response (IL-6, TNF- α, sTNFR1, sTNFR2) and intestinal permeability (zonulin and LPS).
- The participant will receive 75 g of glucose (grape sugar) plus 3g 3-O-Methyl-D-glucose dissolved in 300mL tap water which he/she will have to drink over a period of 5-10min. ("oral glucose tolerance test")
- After 30, 60, 90 and 120min we will again take blood samples for measurement of blood sugar, insulin, C-peptide and 3-OMG. In total we will take a maximum of 30mL blood (corresponding to 3 tablespoons).
- During this appointment we will fill in the questionnaire for gastrointestinal symptoms together with the participant.
- At the end of the visit, the participant will receive the portioned sweeteners (if assigned to one of the polyol groups) and the kit for the second faecal sample.

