8.3.5 Third Visit = 2. Metabolic visit

The third visit (2. metabolic visit) at our outpatient clinic will take about 2.5 hours.

We will carry out an oral glucose tolerance test and take blood and urine samples. Again, the participant has to arrive on an empty stomach (not allowed to eat or drink 10 hours prior to this appointment except for tap water or unsweetened herbal tea without milk). Even chewing gum must be avoided, as they might contain sugar. In addition 2 days prior to the test the participant has to refrain from heavy physical activity and needs to have carbohydrates as part of her/his meals.

- The participant must bring along his/her study folder, the remaining sweetener portions and the second stool sample if possible.
- We will briefly examine the participant (measurement of blood pressure, weight).
- We will take a first blood sample to measure blood sugar, insulin, C-peptide (for the oral glucose tolerance test). In addition we will measure biomarkers of inflammatory response (hsCRP, IL-6, TNF-α, sTNFR1, sTNFR2) and intestinal permeability (zonulin and LPS) and measure ALAT, ASAT, blood lipids and leucocyte count.

- The participant will receive 75 g of glucose (grape sugar) plus 3g 3-O-Methyl-D-glucose dissolved in 300mL tap water which he/she will have to drink over 5-10min. ("oral glucose tolerance test").
- After 30, 60, 90 and 120min we will again take blood samples for measurement of blood sugar, insulin, C-peptide and 3-OMG levels. In total we will take a maximum of 30mL blood (corresponding to 3 tablespoons).

SCHEDULE OF ASSESSMENTS (FLOW OF RESEARCH PROJECT)

Project Periods	Screening Visit (V1)	Baseline Metabolic Visit (V2)	Intake of sweetener: • erythritol or xylitol • week 1: adaption					Follow-up Metabolic Visit (V3)		
Location	St. Claraspital	St. Claraspital		eek			JUIOI			St. Claraspital
Time (hour, day, week)	-7d	0d	3	x/da	ay					49d +max. 3 days
			Weeks							
			1	2	3	4	5	6	7	
Participant Information and Informed Consent	х									
Demographics: weight, height, abd. circumference	х									x
Medical History	х									
In- /Exclusion Criteria	х									
Randomization		х								
Fasting blood sample	х	х								х
Haemoglobin	х									
• Leucocytes	х									х
• HbA1C	х									
Liver enzymes: ALAT, ASAT	х									x
Creatinine	х									
Lipid panel (Triglyc., total Chol., HDL, LDL)	х									х
• hsCRP	х									х
 Serum aliquots for: IL-6, zonulin TNF-α sTNFR sTNFR2 LPS 		х								x
Urine Pregnancy Test	х									

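### Lipids, liver enzymes, hsCRP and leucocytes have their only pre-treatment sample at screening, under looser preparation than the follow-up sample, so their within-arm before-after tests do not compare like with like

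*Protocol*

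**What the plan says.** Lipids, liver enzymes, hsCRP and leucocytes are secondary outcomes in Protocol 4.2, where the inflammatory outcome includes "high sensitive CRP (hsCRP) and leucocytes" beside IL-6, TNF-α, sTNFR1 and sTNFR2. Section 8.2.2 has lipids, liver enzymes and hsCRP measured at baseline and after treatment. Section 5.1 lists the OGTT, liver enzymes and blood lipids together as one metabolic work-up at baseline and at 7 weeks.

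The visit sections divide that work-up:

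- V1, day -7 (8.3.1): "We will take a blood sample and examine HbA1C, creatinine, ALAT, ASAT, hsCRP and blood lipids". Leucocytes are not in this list, but both schedule tables mark them at V1.
- V2, day 0 (8.3.2): glucose, insulin and C-peptide, then "In addition we will measure biomarkers of inflammatory response (IL-6, TNF- α, sTNFR1, sTNFR2) and intestinal permeability (zonulin and LPS". Lipids, liver enzymes, hsCRP and leucocytes are absent here and unmarked in the V2 column of the schedule.
- V3, day 49 plus at most 3 days (8.3.5): the OGTT samples and inflammatory markers including hsCRP, and "and measure ALAT, ASAT, blood lipids and leucocyte count".

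Preparation for V1 is a fast: "not allowed to eat or drink 10 hours prior to this appointment except for tap water or unsweetened herbal tea without milk". For V3 the same fast applies, and "In addition 2 days prior to the test the participant has to refrain from heavy physical activity", with carbohydrate in meals. Section 8.2.1 sets the general OGTT rules, including "to abstain from strenuous exercise within the last 48h before OGTT", no smoking or alcohol for 10 hours, and no acute illness in the preceding 14 days.

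Section 10.4.1 has each sweetener participant serve as his or her own control, expects similar results at the control arm's two time-points, and compares post-treatment values with control. Section 10.4.2 names a paired t-test for before versus after, with significance at P < 0.05.

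**The concern.** A before-after comparison is fair only if both samples are taken under the same conditions. For eight measures (triglycerides, total cholesterol, LDL, HDL, ASAT, ALAT, hsCRP, leucocytes) the before sample follows a fast alone and the after sample follows the fuller OGTT preparation. A systematic shift from this difference would enter the paired test as if it were a sweetener effect. It could also make the control arm's two time-points differ although nothing was given.

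The inflammatory outcome is split as well: IL-6, TNF-α and the two receptors have a day-0 baseline, while hsCRP and leucocytes have a day -7 baseline. What is at stake is the reading of within-arm changes in these secondary outcomes, which the pilot is meant to pass on to larger studies.

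**Working it through.** The protocol states no power or error figure for these outcomes, so there is none to reproduce. The check has two parts.

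**1. Preparation, rule by rule**

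| Rule | V1 (8.3.1) | V3 (8.2.1, 8.3.5) | Difference |
|---|---|---|---|
| Fasting | 10 h | 10 h | none |
| Alcohol | barred for 10 h, since only water or unsweetened herbal tea is allowed | barred for 10 h | none |
| Strenuous exercise | no rule | 48 h | yes |
| Carbohydrate in meals | no rule | 48 h | yes |
| Smoking | no rule | 10 h | yes |
| Acute illness | no rule of its own | 14 days | partial |

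On illness, the OGTT rule also applies at V2 on day 0 and reaches back to day -14. With V1 at day -7 it covers 14 - 7 = 7 days before V1. Relative to V3, the week from day -21 to day -14 is uncovered. Nothing says that the V1 sample is redrawn if a participant was ill at that time and V2 was postponed.

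**2. What a shift would do to the paired test (illustration)**

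Inputs: n = 20 per arm (10.2); significance level 0.05 (10.4.2), taken as two-sided because the protocol does not say; no sweetener effect; a mean preparation shift of k SDs of the within-person change. The values of k are assumptions.

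The test statistic follows a noncentral t distribution with 19 degrees of freedom and noncentrality k√20. The critical value is 2.093. The false-positive rate is 1 - F(2.093) + F(-2.093), where F is that distribution's cumulative function.

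| k | k√20 | False-positive rate |
|---|---|---|
| 0 (matched preparation) | 0 | 5.0% |
| 0.1 | 0.447 | 7.1% |
| 0.2 | 0.894 | 13.6% |
| 0.3 | 1.342 | 24.7% |
| 0.5 | 2.236 | 56.5% |

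**Comparison with control.** Section 10.4.1 compares post-treatment values, so the V1 value does not enter. If change were compared instead, a shift common to both arms cancels: in 40,000 simulated trials of 20 versus 20, a two-sample t-test on change rejected in 5.0% at k = 0.3 and in 5.0% at k = 0.5.

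**Primary outcome.** The OGTT is done at V2 and V3 under the same rules, so it is unaffected.

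**The case against.** The strongest reply is that the control arm contains the problem. Controls go through all assessments (7.2.2), so they carry the same V1-to-V3 difference. A preparation shift would show in them and would help a reader recognise it. This stands, and it limits the point to the within-arm tests. It does not remove it, because 10.4.2 tests each sweetener arm against its own earlier values at P < 0.05. Section 10.1 calls hypothesis testing not applicable in this exploratory study, but 10.4.2 sets a significance threshold all the same.

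A second reply is that a screening panel is reasonable in itself: 6.1 requires otherwise healthy volunteers, and 8.3.1 uses V1 to establish eligibility. That is fair. The point is not that the tests are done at V1, but that V1 supplies the outcome baseline.

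Several stronger readings are tempting and are not supported:

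- A reader might infer that alcohol rules differ. They do not; the V1 fast bars it for the same 10 hours.
- A reader might infer that V1 has no protection against recent illness. The V2 rule covers the week before V1.
- A reader might infer that the stricter preparation lowers these measures and so mimics a benefit. The documents give no direction or size.
- A reader might infer that comparisons between arms are biased. They are not, as the working shows.
- A reader might infer that no baseline leucocyte count will exist. Section 8.3.1 omits it, but both schedule tables include it; this is an inconsistency to correct.

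**Conclusion.** The point holds in a limited form. Eight measures across the lipid and liver-enzyme outcome and the inflammatory outcome have a pre-treatment value taken a week before the visit named as baseline, without the exercise, carbohydrate and smoking rules of V3 and with only part of its illness rule. Their paired before-after tests cannot separate preparation from sweetener effect. This also sits badly with 5.1, which presents liver enzymes and lipids as part of the same baseline work-up as the OGTT.

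The size is unknown. The range of about 7% to 56% false positives rests on assumed shifts of 0.1 to 0.5 SD of the change, 20 analysed participants per arm, a two-sided 5% level, and the reading that the tests in 10.4.2 apply to the secondary outcomes, since the protocol names no others. If preparation has no systematic effect, the rate stays at 5%. Neither the primary outcome nor the comparison with control is put in doubt. This is an inexpensive improvement to secondary outcomes, not a threat to the trial's main result.

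**What to change.** Draw lipids, ALAT, ASAT, hsCRP and leucocytes at V2 from the fasting sample, before the glucose drink, and define V2 as the baseline for these outcomes. Any V1 values then serve screening only. V2 already takes fasting blood under the OGTT preparation rules, and V3 takes these same panels within the 30 mL maximum that is also stated for V2.

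Align both schedule tables with 8.3.1 and 8.3.2. If leucocytes remain a V1 screening test, add them to the list in 8.3.1.

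The cost is protocol wording and, if V1 values are also kept, one extra routine panel per participant. If the tests simply move from V1 to V2, no assays are added. Under 1.15 the change may need ethics committee approval. The current version is dated September 2017 and the planned start was August 2016, so enrolment may already have begun. In that case, record for each participant which visit supplied the baseline. For those with only a V1 value, read the within-arm change beside the change in controls.

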8.3.2 Second Visit = 1. Metabolic Visit

The **second visit (1. metabolic visit)** at our outpatient clinic will take about 2.5 hours. We will carry out an oral glucose tolerance test and take blood, and urine samples. If possible, the participant will bring the first faecal sample to this visit. Again, the participant has to arrive on an empty stomach (not allowed to eat or drink 10 hours prior to this appointment except for tap water or unsweetened herbal tea without milk). Even chewing gum must be avoided, as they might contain sugar. In addition 2 days prior to the test the participant has to refrain from heavy physical activity and needs to have carbohydrates as part of her/his meals.

- The candidate will be assigned randomly to one of the three groups (intake of xylitol, or erythritol or control group).
- The participant needs to bring his/her study folder along, including the food diary which he/she should have kept over the course of 1 week.
- If possible, the participant will bring along the first faecal sample
- We will take a first blood sample to measure blood sugar, insulin, C-peptide (for the oral glucose tolerance test). In addition we will measure biomarkers of inflammatory response (IL-6, TNF- α, sTNFR1, sTNFR2) and intestinal permeability (zonulin and LPS).
- The participant will receive 75 g of glucose (grape sugar) plus 3g 3-O-Methyl-D-glucose dissolved in 300mL tap water which he/she will have to drink over a period of 5-10min. ("oral glucose tolerance test")
- After 30, 60, 90 and 120min we will again take blood samples for measurement of blood sugar, insulin, C-peptide and 3-OMG. In total we will take a maximum of 30mL blood (corresponding to 3 tablespoons).
- During this appointment we will fill in the questionnaire for gastrointestinal symptoms together with the participant.
- At the end of the visit, the participant will receive the portioned sweeteners (if assigned to one of the polyol groups) and the kit for the second faecal sample.

8.3.3 Intake of polyols

Intake of sweetener: After the first two appointments; after taking blood and the first faecal and urine sample, and after filling in the questionnaire for gastrointestinal symptoms and keeping the food diary over 7 days the participant will be ready to start with the sweetener intake. Participants assigned to the control group receive no sweetener.

8.3.4 Follow-up appointments

Appointment: The follow-up visit (3rd visit) will take place in the eighth week. As it can be difficult to make an appointment directly on the first day of week 8, we will provide the participant with some extra sweetener portions to bridge the gap until the visit. There shouldn't be more than 3 extra days. The participant needs to continue with the sweetener intake until the last visit.

8.3.5 Third Visit = 2. Metabolic visit

The third visit (2. metabolic visit) at our outpatient clinic will take about 2.5 hours.

We will carry out an oral glucose tolerance test and take blood and urine samples. Again, the participant has to arrive on an empty stomach (not allowed to eat or drink 10 hours prior to this appointment except for tap water or unsweetened herbal tea without milk). Even chewing gum must be avoided, as they might contain sugar. In addition 2 days prior to the test the participant has to refrain from heavy physical activity and needs to have carbohydrates as part of her/his meals.

- The participant must bring along his/her study folder, the remaining sweetener portions and the second stool sample if possible.
- We will briefly examine the participant (measurement of blood pressure, weight).
- We will take a first blood sample to measure blood sugar, insulin, C-peptide (for the oral glucose tolerance test). In addition we will measure biomarkers of inflammatory response (hsCRP, IL-6, TNF-α, sTNFR1, sTNFR2) and intestinal permeability (zonulin and LPS) and measure ALAT, ASAT, blood lipids and leucocyte count.

- The participant will receive 75 g of glucose (grape sugar) plus 3g 3-O-Methyl-D-glucose dissolved in 300mL tap water which he/she will have to drink over 5-10min. ("oral glucose tolerance test").
- After 30, 60, 90 and 120min we will again take blood samples for measurement of blood sugar, insulin, C-peptide and 3-OMG levels. In total we will take a maximum of 30mL blood (corresponding to 3 tablespoons).

SCHEDULE OF ASSESSMENTS (FLOW OF RESEARCH PROJECT)

Project Periods	Screening Visit (V1)	Baseline Metabolic Visit (V2)	Intake of sweetener: • erythritol or xylitol • week 1: adaption					Follow-up Metabolic Visit (V3)		
Location	St. Claraspital	St. Claraspital		eek			JUIOI			St. Claraspital
Time (hour, day, week)	-7d	0d	3	x/da	ay					49d +max. 3 days
			Weeks							
			1	2	3	4	5	6	7	
Participant Information and Informed Consent	х									
Demographics: weight, height, abd. circumference	х									x
Medical History	х									
In- /Exclusion Criteria	х									
Randomization		х								
Fasting blood sample	х	х								х
Haemoglobin	х									
• Leucocytes	х									х
• HbA1C	х									
Liver enzymes: ALAT, ASAT	х									x
Creatinine	х									
Lipid panel (Triglyc., total Chol., HDL, LDL)	х									х
• hsCRP	х									х
 Serum aliquots for: IL-6, zonulin TNF-α sTNFR sTNFR2 LPS 		х								x
Urine Pregnancy Test	х									
Oral glucose tolerance test 75g glucose (0-30- 60-90-120min)		х								х
Blood glucose		х	-							х
Insulin		х	1							х
C-peptide		х	ses:							Х
3-O-Methyl-D-Glucose		х	j op r							Х
Urine sample		х	3.50) -0.0) -1-0)							Х
Faecal sample		х	n (1-C ns (1-C							Х
GSRS: questionnaire gastrointestinal symptoms	х		Adaption week with increasing doses: • 2 days 1 portion (1-0-0) • 3 days 2 portions (1-1-0) • 2 days 3 portions (1-1-1)		х				х	
Food diary		х	reek days days days		х				х	
Follow-up calls			0 N N	х	х	х	х	х	х	
SAE			laptio	х	х	х	х	х	х	Х
End of study meeting			PΑ							х

